2. Evaluate pre -post and weekly changes in measures of parental emotion regulation, parenting **stress, parenting quality and children's mental health**. Across all parents enrolled in DBT+PT, we will evaluate the rate and pattern of change in these interlinked domains which represent risk factors for relapse and further adverse outcomes. We anticipate pre-post changes (2 time points, approximately 20-22 weeks apart) will be comparable to well-established change scores from the clinical trial literature base for DBT Skills and parent training interventions. Additionally, qualitative data from exit interviews with each parent will be analyzed using thematic analyses of responses to evaluate parents' perceptions of changes in their own mental health, their parenting and their children's behavior over the course of the intervention.

Weekly repeated measures (20 time points) will allow us to model the rate and pattern of change from week to week. As the intervention is divided into 4 modules (see Procedures), change patterns will also be examined between modules. Data will be presented descriptively and we expect changes to unfold in a cascading order, with increased use of skills preceding reductions in parent emotion dysregulation, followed by improvements in parenting quality and subsequent improvements in child behavior.

C. Methods, Materials and Analysis

Setting. Clinical intakes, the weekly group DBT Skills+PT intervention sessions, and exit interviews will all be conducted via a HIPAA compliant teleconference platform (i.e. Zoom). The initial online screener, and pre-post and weekly assessments will be conducted via UO Qualtrics questionnaires.

Study design. This study utilizes a mixed methods case study design with continuous assessment of quantitative measures. Figure 1 presents the study phases, along with what participating parents will complete in each phase, and the estimated time needed to complete each phase.

	time required of participants.	Time Estimate
Study Phase Recruitment	Participant action Parents respond to recruitment	N/A
Reciditment	materials	
↓		
Initial Online Screener	Parent completes:	
	DERS	DERS – 5 minutes
	CAGE-AID	CAGE-AID – 2 minutes
		Total: 7 minutes
•		
Clinical Intake	Parent completes:	Demographica 4 minutes
_	Demographic questionnaire	Demographics – 4 minutes
	PHQ-9	PHQ-9 - 3 minutes
	PPVT-V (Q-Global) SCID 5 diagnostic interview	PPVT-V – 20 minutes SCID 5– 180-300 minutes
		Total: 207-327 minutes
.		

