Following this, parents will complete a demographic questionnaire, the Peabody Picture Vocabulary Test-V (PPVT-V Q-Global), the Patient Health Questionnaire for Depression (9-items; PHQ-9), and the Structured Clinical Interview for DSM-5 (SCID 5). Parents will be ineligible to participate if they meet for the exclusionary criteria detailed in section D. Research Population & Recruitment Methods: Participants.

Pre-intervention Assessment. Parents who meet criteria for the study following the clinical intake will be asked to complete a broad battery of questionnaires (see Fig 1. Study Phase: *"Pre-intervention"*) to assess parent mental health symptoms, parenting stress, parenting quality and child mental health symptoms. The questionnaires will be completed online via UO Qualtrics and parents will receive an encrypted email (i.e. Hushmail) from the project coordinator with the UO Qualtrics link.

DBT Skills +PT intervention. The study plans to recruit three groups of approximately 4-5 parents/group. Parents will be recruited twice throughout the course of the year to facilitate running up to three groups (see section D. Research Population & Recruitment Methods for more details). Once a group of parents has been recruited, participants will take part in 20 weekly DBT Skills +PT intervention sessions. The group sessions are conducted remotely over a HIPAA compliant version of Zoom and groups are led by [name] (PI) and three other doctoral level student co-leaders who are supervised by [name], a licensed clinical psychologist who is trained in both DBT and parent training. [name] [name] (Co-I) and [name] (Faculty Advisor) may also be consulted and provide supervision, when needed.

Prior to the start of the first session, co-leaders will conduct 1 hour individual orientation sessions over Zoom with each participating parent, in order to orient them to the intervention, review intervention related portions of the consent form, and provide participating parents with an opportunity to ask questions in private if they wish.

Before each weekly session, parents will receive an encrypted email from the project coordinator asking them to complete the 5 measures listed in Fig. 1: Study Phase: "Treatment Phase", via a set of online UO Qualtrics questionnaires.

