The DBT Skills +PT group intervention is a novel integration of three evidence-based treatments (i.e. DBT Skills, Parent Management Training (PMT), and Emotion Coaching (EC)). Each DBT Skills +PT session will last up to 2.5 hours. The structure of each session typically includes a brief mindfulness practice, homework review to discuss use of skills previously learned, a 10-15 minute break, didactics to learn a new set of DBT and PT skills, and assignment of homework. The DBT Skills portion of each session follows the DBT Skills Training Manual Second Edition (Linehan, 2015a) and DBT Skills Training Handouts and Worksheets Second Edition (Linehan, 2015b). The DBT Skills portions cover the four modules of traditional DBT Skills, which each focus on specific goals related to emotion regulation:

- 1) Mindfulness Skills help clients increase control over their attention and notice present emotions and thoughts. These skills are taught for 2 weeks at the start of the other three modules.
- 2) Emotion Regulation Skills teach skills to understand and label emotions, decrease the frequency of unwanted emotion, and decrease emotional vulnerability.
- Distress Tolerance Skills teach clients how to deal with the most intense emotions in which they have urges to self-destruct. One set of distress tolerance skills is specifically focused on managing difficulties with addiction.
- 4) Interpersonal Effectiveness Skills help clients apply ER skills within interpersonal contexts, which are often highly emotionally evocative for individuals with elevated emotion dysregulation.

Parent training portions (both PMT and EC components) follow the Parenting Hyperactive Preschoolers Clinician Guide (Harvey, Herbert & Stowe, 2015) which was selected because it is an evidence-based parent training program that integrates PMT and EC (Herbert et al., 2013). Parent management training (PMT) portions of the intervention cover: how to use praise effectively, how to

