We will examine change across time based on data available in the weekly assessment measures of parents' DBT and parenting skill use (DBT-WCCL, Skill Use Diary Card), parents' emotion dysregulation (DERS), parenting quality (PS), and children's symptoms and behaviors (ERC and WACB). Consistent with common practice in case study designs (Kazdin, 2003; Kazdin, 2019; Rizvi & Nock, 2008), we will primarily use visual inspection (i.e. evaluating graphical displays of participants' weekly scores) to examine the data collected during Weeks 1-20 of the DBT Skills +PT intervention. We will use the same procedures to examine changes in data collected at the four time points representing the start of each DBT module. We will inspect several aspects of these data, such as changes in the trajectories of each measure, to determine the direction and extent of change in the measured symptoms and behaviors from week to week, and the timing of when those changes occurred. We will also characterize the order in which changes unfold over time (e.g. increased DBT skill use precedes improvement in parent emotion regulation, which precedes improvements in parenting quality measures, which precedes improvements in child behavior measures). These visual inspection analyses will be conducted at both the individual level and at an aggregated group level.

We will employ a number of standard methods of statistical analysis of single-case experimental design (SCED) data to further examine, quantify and corroborate results of visual inspection. Consistent with previous SCED studies, we will calculate Tau-U effect sizes (Parker et al., 2011; Vannest & Ninci, 2015; Brossart et al., 2018), linear regressions (Ramaiya et al., 2018) and perform hierarchical linear modeling which can be used to aggregate single-case results (Van den Noortgate & Onghena, 2007; Ugille et al., 2012). These analyses will provide preliminary information on the rate and order of change for the different targeted symptoms and behaviors, and enable us to report on the degree to which DBT Skills +PT changed parent-reported symptoms and behaviors at the level of individual parents as well as at the group level, aggregating data across all participating parents.

D. Research Population & Recruitment Methods

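### The between-module look uses only four module-start scores, so it shows no change for the last module; a closing point from data already collected would supply it

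*Combined protocol and SAP*

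**What the plan says.** Section B (Specific Aims, Aim 2) sets the goal: "As the intervention is divided into 4 modules (see Procedures), change patterns will also be examined between modules". Section C (Analyses, Aim 2) first plans visual inspection of every weekly score over Weeks 1-20 and then adds the module look, which applies the same inspection to "data collected at the four time points representing the start of each DBT module".

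The teaching sequence is in Section C (Procedures, DBT Skills +PT intervention). There, "The DBT Skills portions cover the four modules of traditional DBT Skills", and of mindfulness it says "These skills are taught for 2 weeks at the start of the other three modules". The same section fixes the length, as "participants will take part in 20 weekly DBT Skills +PT intervention sessions", and the timing of measurement: "Before each weekly session, parents will receive an encrypted email from the project coordinator" with the link to that week's questionnaires.

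The plan does not give the order of the modules, their lengths, the week in which each starts, or how the repeat mindfulness weeks are to be assigned. It names no closing point for the module look.

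**The concern.** A score taken at the start of a module, before its first session, is a baseline for that module. It also closes whatever came before. A set made up only of starts therefore has no closing score for whichever module comes last. One of the four modules drops out of the comparison that Aim 2 promises.

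The intervals that remain are also hard to compare. Mindfulness comes back before each other module, so the stretch from one start to the next need not be one module's teaching, and the stretches differ in length.

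The plan uses visual inspection to judge when change occurs and in what order, for each parent and in aggregate over three groups. If the start weeks and the closing point are not fixed beforehand, they can be placed after the plots have been seen, and they need not be the same across groups.

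**Working it through.** **Inputs from the plan.** 20 weekly sessions and 20 weekly measurements; four named modules; mindfulness taught for 2 weeks before each of the other three; questionnaires requested before each session.

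**Assumptions.** The DBT sequence fills all 20 weeks. The three non-mindfulness modules last L1, L2 and L3 weeks in the order taught, each between 3 and 6 weeks. The plan gives no lengths.

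**Step 1: weeks available.** Mindfulness takes 3 × 2 = 6 weeks. The rest is 20 - 6 = 14 weeks, so L1 + L2 + L3 = 14, an average of 14/3 = 4.7 weeks each.

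**Step 2: can the plan's four starts be reproduced?** Three ways of counting, with week numbers for an assumed 5/5/4 split:

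| Reading | Starts | Weeks (5/5/4) |
|---|---|---|
| Mindfulness opens each of three blocks | 3 | 1, 8, 15 |
| Every return to mindfulness is its own start | 6 | 1, 3, 8, 10, 15, 17 |
| First mindfulness week, plus first content week of each other module | 4 | 1, 3, 10, 17 |

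Only the third reading gives four.

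**Step 3: intervals on that reading.** The starts are weeks 1, 3, 5 + L1 and 7 + L1 + L2. The intervals between them are 2, L1 + 2 and L2 + 2 weeks. For 5/5/4 these are 2, 7 and 7 weeks. Over lengths of 3 to 6 weeks, the second and third intervals run from 5 to 8 weeks. The repeat mindfulness share of each is 2/(L + 2): 2/7 = 29% at L = 5, 2/6 = 33% at L = 4, and between 2/8 = 25% and 2/5 = 40% over the whole range.

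**Step 4: what follows the last start.** Four starts give 4 - 1 = 3 intervals. The weeks from the last start to week 20 number 20 - (7 + L1 + L2) + 1 = 14 - L1 - L2 = L3. Near-equal splits (5/5/4, 4/5/5, 5/4/5) give 4 or 5 weeks, which is 20% to 25% of treatment. The wider range gives 3 to 6 weeks, or 3/20 = 15% to 6/20 = 30%. The missing interval does not depend on these lengths, since any set of starts alone leaves its last segment open.

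**Step 5: is there a score that could close it?** Figure 1 lists DERS, DBT-WCCL, PS, ERC, WACB and CCNES at the post-intervention assessment. The first five are also among the weekly measures that the Aim 2 analysis names. CCNES is collected weekly but is not named there. The Skill Use Diary Card is not listed post-intervention, so its last reading is week 20, which is requested before session 20.

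**The case against.** The module look is an addition to a descriptive analysis. The main method uses all the weekly scores, supported by Tau-U, regression and hierarchical linear models, and no test or sample size depends on the four points. The plan does not say that differences between starts will be calculated or credited to a module. Mixed content is part of the design: mindfulness recurs on purpose, and sessions also teach parenting skills, so no division into DBT modules isolates one module's effect. Measuring before the session is not a fault either, since a start score properly closes the preceding interval.

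Most of this stands, and it rules out three stronger conclusions that a reader might draw:

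- That four starts contradict the taught sequence. They do not, because the third reading in the working produces four. What is missing is the rule.
- That the last module has no end data. The weekly scores run to week 20, and the main scales are repeated after treatment. The gap lies only within the four-point set.
- That between-module change cannot be examined at all. Module boundaries can be drawn on the full weekly series.

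The objection does not remove the gap in the look as specified. Four plotted start scores show three stretches of change, and the last module is in none of them. That the analysis is descriptive lowers the stakes but does not supply the missing point.

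**Conclusion.** The point holds as a minor one. As written, the supplementary module look leaves one of the four modules without a change. That conclusion needs only the count of starts and the pre-session timing of the questionnaires.

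On the only one of the three readings that gives four starts, the first interval is 2 weeks and the next two each contain a 2-week return to mindfulness, so the intervals are unequal and mixed. Their exact weeks, and the 3 to 6 weeks after the last start, rest on the assumed module lengths. The main weekly analysis and the pre-post comparison are unaffected.

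**What to change.** - Add a fifth, closing point to the module look: the post-intervention assessment for DERS, DBT-WCCL, PS, ERC and WACB (and CCNES if it is included), and week 20 for the Skill Use Diary Card. Note that the week-20 reading precedes the last session, and that the post-intervention assessment may come somewhat later, since Section B puts the pre-post gap at about 20 to 22 weeks.
- Have the investigators state the module sequence and start weeks, and whether these are the same in all three groups.
- Mark the module starts and the repeat mindfulness weeks on the full weekly plots. Compare modules on all weekly scores within each segment instead of single start scores. Use level throughout, and slope only where a segment has enough weeks: a 2-week mindfulness segment has two scores, so its slope is a single difference.

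The cost is a few sentences of analysis wording. No new data or visits are needed.

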Participants. We intend to recruit and conduct intakes with approximately 18 parents, enroll up to 15 eligible parents in DBT+PT, so as to reach our target of 12 parents who complete at least 4 sessions. This attrition rate is based on our lab's prior experience providing DBT Skills to a parent population. Participating parents will be split into three DBT Skills +PT groups that are run at different times over the course of the year. Recruitment efforts will take place twice over the course of the year to facilitate this.

To participate, parents must be 18+ years of age and reside in Oregon, have at least partial custody of a 3-6 year old child, neither parent nor child may have any known developmental disability, and the parent must be proficient in English, as our laboratory is unable to conduct the clinical intake, assessments, and DBT Skills +PT intervention with non-English speaking participants. Parents must also have internet access to facilitate participating in the remote telehealth DBT Skills +PT intervention. Additionally, eligible parents must endorse elevated emotion dysregulation (a score of >88 on the DERS, equivalent to +.5 SD above a normative score; Ritschel, Tone, Schoemann, & Lim, 2015) and endorse 2 or more items on the CAGE-AID screener for past (past 5 years), but not current (not in the past 12 months), substance use.

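### In the group graphs, the week in which a measure visibly moves depends on how much it changes as well as when it starts, so the order-of-change reading needs a size-free companion before a cascade is reported

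*Combined protocol and SAP*

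**What the plan says.** Section C, Analyses, Aim 2 makes graphs the main tool: "we will primarily use visual inspection", applied "to examine the data collected during Weeks 1-20 of the DBT Skills +PT intervention". Among the features to be read is "the timing of when those changes occurred". The order follows from that: "We will also characterize the order in which changes unfold over time (e.g. increased DBT skill use precedes improvement in parent emotion regulation", with parenting quality and then child behavior as the later links. The level of reading is also stated: "These visual inspection analyses will be conducted at both the individual level and at an aggregated group level".

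Section B, Aim 2 commits to the direction beforehand: "we expect changes to unfold in a cascading order, with increased use of skills preceding reductions in parent emotion dysregulation".

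Tau-U, linear regression and hierarchical linear modeling are added to support the visual reading and are said to inform both rate and order. The plan does not define onset or a common scale across measures. It gives no comparison with simultaneous change, no lag or change-point term, and no result that would count against the cascade.

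**The concern.** Two things decide when a plotted series is seen to move: when its change begins, and how fast it climbs out of its own week-to-week scatter. A measure that changes a lot clears the scatter sooner than one that changes a little, even with identical starts. Reading order from visible movement therefore compares the data with equal size and noise of change, not with the absence of temporal order.

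DBT skill use is taught directly and child behavior is the most distant link, so it is plausible that standardized change shrinks along the predicted chain. The artefact would then point towards the stated hypothesis, and a reader could not tell that skills changed first from that they changed most. If sizes run the other way, a real cascade could be hidden. The planned statistics do not settle this, because as described they quantify amount or slope of change, not when it began.

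**Working it through.** **Inputs from the documents.** Twenty weekly points, all during treatment (Section B: "Weekly repeated measures (20 time points) will allow us to model the rate and pattern of change from week to week"); a target of 12 parents (Section D, Participants: "so as to reach our target of 12 parents who complete at least 4 sessions"); four links in the expected order. The documents give no figure for timing or order, so there is nothing to reproduce.

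**Inputs assumed.** Total change per measure, noise, autocorrelation and the rule for visible change.

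**Step 1: arithmetic without noise.** Let a measure change in a straight line from Week 1 to Week 20 by a total of D, and call it visible once it has moved by c. The crossing week is 1 + 19c/D. With c = 0.5 SD:

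- D = 3: 1 + 9.5/3 = 4.2
- D = 2: 1 + 9.5/2 = 5.8
- D = 1.5: 1 + 9.5/1.5 = 7.3
- D = 1: 1 + 9.5/1 = 10.5

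All four start in Week 1, yet they become visible about six weeks apart (10.5 − 4.2 = 6.3). The slope is D/19, so ranking measures by slope repeats the ranking by size.

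**Step 2: simulation with no true order.** Settings: the mean of 12 parents over 20 weeks, all measures linear from Week 1; within-parent noise SD 0.3 or 0.5 with autocorrelation 0.3; between-parent SD of change 0.3. Visible onset is the first of two consecutive weeks at least 0.2 or 0.3 SD better than the mean of Weeks 1–3. Repeat runs moved the ends of the ranges by about a percentage point.

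| Total change: skill / DERS / parenting / child (SD) | Skill before child | Full four-step order |
|---|---|---|
| 0.6 each | 44–47% | 2–3% |
| 0.8 / 0.7 / 0.6 / 0.5 | 61–79% | 5–10% |
| 1.0 / 0.8 / 0.6 / 0.4 | 73–94% | 8–23% |
| 1.2 / 0.8 / 0.5 / 0.3 | 82–98% | 13–39% |

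Because of tied weeks, the equal-size row falls below 1/2 and 1/24 = 4.2%.

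A second set of assumptions (noise SD 1; changes of 3/2/1.5/1; rules of 0.5 SD, 1 SD or 2 SE) gave skill before child in 88–99% and the full order in 17–51%. The upper figure counts a last measure that never crosses. Equal changes gave about 43% and 1–2%.

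**Step 3: other conditions.**

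- Sizes reversed (1.2/1.5/2/2.5): skill before child in only 2–14% of group-level trials.
- A true cascade with sizes 0.4/0.6/0.8/1.0: visible onset recovered the full order in 37–62%, against 65–89% for area-based timing.
- Single parents: the full order appeared in 2–4% under the first settings and 4–7% under the second. Under the second, the skill-before-child comparison alone still ran at 56–89%.

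**Step 4: candidate size-free timings.** Rescale each group-mean series as p(t) = (score − mean of Weeks 1–3) / (mean of Weeks 18–20 − mean of Weeks 1–3). For the straight line, the Weeks 1–3 mean is D/19 and the Weeks 18–20 mean is 18D/19, so p(t) = (t − 2)/17 and D cancels. The area time, the sum of 1 − p(t) over the 20 weeks, is 20 − (210 − 40)/17 = 10 for every D.

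In the Step 2 settings:

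- Area-based time: skill before child 49–51%, full order 4–6%, in every row.
- First week in which half of the total change is reached: with unequal sizes, skill before child 29–32%, 19–23% and 11–16% as the spread widens, and the full order in at most 1.4%. Small, noisy series reach their own halfway mark early by chance, so this rule is biased the opposite way.

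**The case against.** The onset rule used above is not the plan's. The plan inspects several aspects of the trajectories, and a careful rater might call four straight lines from Week 1 simultaneous. Sizes and noise are assumed, and mild differences in size give the full order in only 5–10%. The results are described as descriptive and preliminary, in a pilot that disclaims any need for inferential analysis. All of this stands. It limits the consequence and rules out treating the percentages as a forecast. It does not remove the confounding, because nothing in the plan tells the rater how to separate size from timing.

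The objection to replacing visual inspection also stands. Area-based time measures the midpoint of change, not onset. In simulations of a true onset cascade in which skills grow gradually while later links change quickly, with sizes falling along the chain, it recovered the full order in 0–3%, against 9–49% for visible onset. It also needs late-week scores, while the recruitment target counts parents who complete as few as four sessions. It can serve as a check on the graphs, not as a substitute for them.

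A reader might infer that any cascade this study reports would be spurious, or that the method always favors the hypothesis. The documents support neither: they give no effect sizes, and the direction of the artefact follows the ranking of those sizes.

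**Conclusion.** The point holds for the group-level reading of order. With no true order and standardized change shrinking along the chain, the aggregated graphs put skill use before child behavior in about 60–98% of simulated trials and show the full cascade in 5–39%, against about 45% and 2–3% when sizes are equal. These figures rest on assumed sizes, noise and a visibility rule. With reversed sizes the apparent order reverses.

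It does not extend to the direction or extent of change, which the graphs can show. It extends only weakly to individual graphs, where the full order appears in 2–7%. It is not a reason to abandon visual inspection. What follows is a limit on the order claim and an inexpensive companion analysis.

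**What to change.** Keep the visual inspection as planned, and add the following to Section C, Analyses, Aim 2:

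1. A group-level companion display and summary, with each weekly measure's group-mean series rescaled to the proportion of its own total change, as in Step 4, and timed by the area-based time. Do not use the first week at which half of the change is reached.
2. A comparison of the observed order with simultaneous change: 1/2 per link and 1/24 for the full order for the area-based time, or values simulated from the fitted group curves.
3. A reporting rule: state a temporal order only when the raw and rescaled readings agree. Otherwise state that size and timing cannot be separated.
4. A sentence that individual-level order is illustrative.

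The cost is analysis wording and a short script, with no new data, visits or participants. The plan should state the downsides. The area-based time marks the midpoint of change and can miss a cascade in which skills grow gradually and later links change quickly. It is unstable when total change is small. It depends on scores from the last weeks, so the number of parents contributing to each curve should be reported.
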